The study research coordinator will identify medications errors and adverse drug events within both arms, but clinicians will not be privy to this information as part of usual care. However, usual care and follow up will ensure all patients in both arms receive the most up to date and effective care that is provided in the current health care environment. Should these identified, but not acted upon, medication safety issues induce patient

harm, it will be closely tracked by the research personnel and reported as detailed in the DSMP. Through this plan, we are minimizing all potential risks for patients participating in this study.

Unknown Risks: The researchers will inform patients if they learn anything that may alter patient's views about participating in the study. Since all patients in both arms of this study are receiving standard of care, no additional risks are foreseen with this study.

Adequacy of Protection Against Risks

Recruitment and Informed Consent

Participation in the study will be voluntary. Patients who have received a renal transplant 6 to 36 months post-transplant will be identified during routine clinic visits for usual care. Subjects who meet inclusion criteria for the study will be asked about their desire to participate. Patients will be required to complete an informed consent document to ensure they understand the goals, risks, and potential benefits of the study before any research related activities occur.

Protection against Risk

There should not be any extensive risks to patient safety during the completion of this study: no investigational medications will be used and all changes to patient's current medication regimens will be made in accordance with and under the direct approval of a transplant physician. In order to protect subjects against any risk regarding loss of personal information, all obligations under the Health Information Portability and Accountability Act (HIPAA) will be met. Additionally, all data will be collected and stored through the secure network server and behind the MUSC firewall. We will use electronic CRF forms approved by the IRB to gather all study information. Data will only be stored on campus computers under the MUSC secure network. Data collection forms will be maintained within an office, which is a locked office facility on campus. Only approved study members will have access to patient data.

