The clinical transplant pharmacist will be alerted by the patient if there are medication changes made by outside providers, by way of making adjustments to the medication regimen in the mobile app. At this point, the patient will be contacted to evaluate the medication change and determine if the adjustment to the regimen is safe and effective. If the pharmacist deems this change to be of concern, they will work with the patient and transplant physician to alter the regimen in an appropriate manner. In addition, the pharmacist will be alerted if the patient has evidence of significant nonadherence ($\geq 20\%$ missed self-reported medication doses in the course of a week), if they have blood pressure or glucose values that fall into critical ranges or if there are alarming trends in their readings or symptom assessments from surveys. Upon receiving these alerts, the pharmacist will communicate with the patient, determine the root cause and coordinate care with other care providers as delineated at the bottom of Figure 4.

[figure not shown]
During televisit encounters, the transplant pharmacist will conduct a thorough medication review, evaluate for signs and symptoms suggestive of medication safety issues, screen for drug-drug and drug-disease interactions and provide recommendations to resolve identified issues to the patient and/or provider, when applicable. The clinical pharmacist will be alerted and evaluate each patient when making a transition of care (inpatient admission or discharge) to ensure accurate medication regimens are communicated to accepting teams and to the patient. The same ambulatory EPIC note template that is used by the clinical pharmacist during the usual care visits will be utilized for documentation during these telehealth encounters. EPIC is the inpatient and ambulatory EHR utilized within the study institution. The process used to resolve medication safety issues during distant monitoring is outlined in Figure 4. Once the clinical pharmacist identifies an issue, they will develop a management plan using the algorithm detailed in Figure 5, discuss the recommendations with the providers, agree on a plan, and implement the plan with direct patient follow-up. The algorithm in Figure 5 encompasses the major medication safety issues, including side effects, adherence, drug interactions and less than optimally controlled comorbid disease states.

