Starting in the top left corner of Figure 6, the medication regimen is created or updated in the EHR by the transplant pharmacist or other qualified healthcare professional. This data flows into the medication app (top middle of figure), through a continuity of care document (CCD), which contains machine-readable patient information. The app accepts CCDs via direct messaging (government sponsored encrypted email), SFTP and FTPS. Upon receipt, the app parses the CCD and uses its data to create a patient friendly medicine schedule, where it is then updated and verified for accuracy by the transplant pharmacist. Once verified, the medication regimen flows into the patient's mobile smartphone device (top right of figure). Each medicine will include its purpose, route of administration, special instructions (e.g., "Avoid grapefruit and grapefruit juice"), possible side effects and adherence record. The smartphone application allows the patient to have an accurate, updated list of their medication regimen, while also providing reminders to take medications at the correct times. Medication reminders will include a checkbox for each medication. The patient will be asked to check the box if

they have taken that medicine. These self-reported responses get tabulated and recorded in the program as an adherence score for that medicine and an overall score for all medicines. As part of this study, the clinical pharmacist will have access to this data in the report dashboard, located on a secure HIPAA compliant website. If the patient changes or updates their medication regimen through the application, an email will be sent to the transplant pharmacist, who will contact the patient to determine the medication, dose and interval and review it as outlined in Figure 4. Once all issues are resolved, the pharmacist will enter the medication into the EHR as a self-reported medication.

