Adverse drug events (ADEs) will be defined according to the AHRQ Patient Safety Network, in which it describes an adverse drug event as “an adverse event (i.e., injury resulting from medical care) involving medication use.(21) The severity of the adverse drug event will be defined according to a modified version 4.0 of the CTCAE developed by the National Cancer Institute. The CTCAE is a standardized classification system developed to assess the frequency and severity of adverse events. It was originally designed for cancer patients, but is now routinely utilized across multiple patient types in clinical research.(48, 49) The modified CTCAE utilized by the study investigators for this study can be found at the end of this document. ADEs will be summarized in DSMP reports and categorized by severity and study arm. These reports will be provided to the IRB on an annual basis.

3.d Classification of Events

Adverse drug events will be classified according to the modified CTCAE, as detailed above.

3.e Data Collection Procedures for Serious Adverse Events and Adverse Drug Events

In both the usual care and intervention arms, a highly trained clinical research coordinator will independently interview all participants at bimonthly intervals to capture and record all medication errors and adverse drug events, including timing, likely cause and severity of each event. These events will be further reviewed and adjudicated by a pharmacist not involved in delivering the study intervention, in a blinded fashion. To assess for medication errors, the research coordinator will review and compare the patient’s documented medication regimen in the electronic health record (the regimen intended to be taken) to the medication regimen actually being taken by the patient, which will be assessed using the patient’s medication bottles and/or lists.

Serious adverse events will be continuously screened for by chart review for new hospitalizations, kidney biopsies, and deaths. The EHR will be utilized, as it has alerting systems capable of screening and notifying the study coordinator and PI of events within study patients.

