1. Medication errors will be defined as documentation that a patient is taking a medication in a manner that was not intended; synonymous with the definition developed by Overhage and utilized within our previous research.(11,14).
2. Adverse drug events will be defined according to the AHRQ Patient Safety Network, in which it describes an adverse drug event as “an adverse event (i.e., injury resulting from medical care) involving medication use”.(21) The severity of the adverse drug event will be defined according to a modified version of the CTCAE developed by the National Cancer Institute and utilized in our previous research. The CTCAE is a standardized classification system developed to assess the frequency and severity of adverse events. It was originally designed for cancer patients, but is now routinely utilized across multiple patient types in clinical research.(48, 49). In both the usual care and intervention arms, a highly trained clinical research coordinator will independently interview all participants at bimonthly intervals and review their medical records to capture and record all medication errors and adverse drug events, including timing, likely cause and severity of each event. To assess for medication errors, the research coordinator will review and compare the patient’s documented medication regimen in the electronic health record (the regimen intended to be taken) to the medication regimen actually being taken by the patient, which will be assessed using the patient’s medication bottles. To assess for adverse drug events, the research coordinator will review patient symptomology, vital signs and laboratory values. Prior to the study being opened for enrollment, the research coordinator will be extensively trained by the study pharmacists in identifying medication errors and adverse drug events, determining causality and grading the severity.

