6. Graft failure will be defined as return to chronic dialysis, transplant nephrectomy, retransplantation or death. The study coordinator capturing clinical event data, different from the coordinator capturing medication error and adverse drug event data (to ensure independence is maintained), will review the medical record at regular intervals to determine if a study patient has developed graft failure. The timing and cause of each graft loss will be recorded for comparative analysis. Patient death will also be captured in a similar fashion, with timing and cause recorded as well.

7. Healthcare encounters will be defined as any direct encounter (face-to-face) between the study patient and a physician or advance practice provider (APP) occurring within a licensed healthcare facility and occurring during the 12-month study. These encounters will be categorized as ambulatory clinic visits, ambulatory procedure visits, acute care/emergency room visits and hospitalizations. Hospitalizations will be defined as an admission to a hospital with at least one overnight stay. Length of stay within the hospital for readmissions will also be captured. Healthcare encounters will be captured through direct study subject interviews with patients at bimonthly intervals.(36) The study coordinator will record all healthcare encounters that have occurred. If the patient has a health care encounter outside of the study institution, the research coordinator will document the type of encounter to estimate costs, as detailed below.

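### The medication-error endpoint is read against an EHR list that the study pharmacist updates in the intervention arm only, so an outside drug taken as directed can count as a discrepancy in control but not in intervention

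*Combined protocol and SAP*

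**What the plan says.** E4 item 1 defines a medication error as "taking a medication in a manner that was not intended". E3 3.e and E4 item 2 give the method for both arms: every two months the coordinator compares the "documented medication regimen in the electronic health record (the regimen intended to be taken) to the medication regimen actually being taken by the patient". E3 3.e then has each event "further reviewed and adjudicated by a pharmacist not involved in delivering the study intervention, in a blinded fashion".

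D3 3.a describes a route into that same list for the intervention arm. The pharmacist learns of "medication changes made by outside providers, by way of making adjustments to the medication regimen in the mobile app", contacts the patient, works with the transplant physician if the change is of concern, and finally, "Once all issues are resolved, the pharmacist will enter the medication into the EHR as a self-reported medication". The app is supplied to the intervention cohort only.

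For discrepancies that the coordinator finds in either arm, D2 2.f says that "clinicians will not be privy to this information as part of usual care". In control, therefore, the EHR list is updated through usual care alone.

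F1 plans on 64% of control patients having an error in the year, a 50% reduction, and 92% power with 52 per arm. F3 and F4 compare the incidence by Fisher's exact or Pearson's chi-squared test. Neither has an analysis directed at how the reference list was built.

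**The concern.** The EHR list is the yardstick for this part of the primary outcome, and the intervention edits it in one arm. Suppose that a community physician starts a drug and two patients, one per arm, take it exactly as told. The intervention patient enters it in the app, the pharmacist accepts it, and it is on the EHR list at the next assessment, where it matches. The control patient's list does not show it until usual care records it, so an assessment before then finds a discrepancy. Both patients behaved identically.

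Keeping the coordinator and adjudicator blind protects against differential judgement. It does not help when the document they consult differs by arm. The safeguards in E3 3.e are explained as preventing higher capture in the intervention arm, and this mechanism more likely works the other way. At stake is whether a reported reduction means fewer mistakes in taking medicines or, in part, a more complete chart.

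**Working it through.** **Inputs from the plan (F1):** control rate 64%; intervention rate 64% × (1 − 0.50) = 32%; 52 per arm; two-sided alpha 0.05.

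**Reproducing the plan's power.** With a pooled variance under the null:

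power = Φ{[d − 1.96·√(2p̄(1−p̄)/n)] / √[(p₁(1−p₁) + p₂(1−p₂))/n]}

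- d = 0.32 and p̄ = 0.48, so √(2 × 0.48 × 0.52/52) = 0.0980, and 1.96 × 0.0980 = 0.1920.
- The denominator is √[(0.2304 + 0.2176)/52] = 0.0928.
- Φ(0.1280/0.0928) = Φ(1.379) = 0.916, in line with the stated 92%.

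Exact enumeration of all 2×2 tables with Pearson's test gives 0.929. That method is used below.

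**Assumed inputs (not in the documents).** Let s be the share of error-positive patients whose only error in 12 months is a record gap, and c the share of such gaps closed by the pharmacist's EHR entry in the intervention arm.

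**Illustration with no true effect on medicine-taking.** The control rate is 0.64 and the measured intervention rate is 0.64 × (1 − s·c). With c = 1 this gives 0.608, 0.576, 0.512 and 0.448 for s = 5%, 10%, 20% and 30%. The table shows the chance of p<0.05 favouring intervention. It is 2.7% with no gaps.

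| s | all gaps close (c = 1) | half close (c = 0.5) | a quarter close (c = 0.25) |
|---|---|---|---|
| 5% | 6% | 4% | 3% |
| 10% | 11% | 6% | 4% |
| 20% | 29% | 11% | 6% |
| 30% | 54% | 18% | 8% |

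**Which part of the table is plausible?** B1 says that errors are usually unintentional non-adherence, which points to a low s. A patient counts in s only if a record gap is the sole error across six assessments. A c near 1 needs nearly every change to be entered in the app and reviewed before the next assessment. F1 expects 18.4 control encounters a year, one every 365/18.4 = 19.8 days, each a possible occasion to update the list. However, E4 item 7 provides for cases where "If the patient has a health care encounter outside of the study institution", and those need not update the study EHR. The upper rows are therefore the more relevant ones.

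**Power of an analysis that excludes record gaps.** For a 50% cut in the remaining errors, compare 0.64(1 − s) with 0.32(1 − s) at 52 per arm. Power is 93% at s = 0, and 90%, 87%, 79% and 69% at s = 5%, 10%, 20% and 30%.

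**The case against.** Four arguments weigh against the point.

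- **The definition already excludes a pure record gap.** A drug taken as its prescriber directed does not plainly meet E4 item 1, and the blinded adjudicator could reject it. This stands as a possible remedy. But the stated method labels the EHR list as the intended regimen, and no visible rule tells the adjudicator to look past it.
- **Cause is already recorded.** The coordinator notes the likely cause of each event, and the primary aim in C1 includes comparing etiologies by arm. G2 promises detailed algorithms to the coordinators, which are not in the text available here. This stands in large part. A reader might infer that the planned data cannot separate fewer mistakes from a fuller chart; the documents do not support that. They could, provided that this cause has its own code, and no visible text says that it does.
- **Reconciliation is the treatment.** Stopping or correcting an unsafe outside drug is a genuine benefit and should be credited. The point concerns only drugs accepted unchanged and then listed.
- **The size is conjecture.** Agreed: s and c are both assumed. A reader might fix on the 29% and 54% cells, but they need a large share and every gap closed. Direction is likely rather than certain, because a fuller list also offers more drugs on which an omission can be found.

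A reader might also see bias in E3 3.e allowing "medication bottles and/or lists" where E4 item 2 names bottles alone. That is a separate wording difference, and nothing shows that it acts differently by arm.

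**Conclusion.** The asymmetry is in the text. The reference list for medication errors is updated by a study route in one arm only, and blinding does not equalise it. How far this moves the result is unknown and may be little. For shares of 5–10%, the chance of a false positive favouring intervention rises from 2.7% to about 6–11% if every gap closes, and to about 3–6% if half or fewer do. This rests on the plan's 64% and 52 per arm, no true effect, and two assumed shares. It does not show that the primary comparison is invalid or that an observed reduction would be an artefact. It shows that one identifiable cause should be coded separately from the start, since whether a drug was taken as its prescriber directed may not be recoverable later.

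**What to change.** 1. In E3 3.e and E4, have the coordinator and the blinded adjudicator, in both arms, code a drug taken as its prescriber directed but absent from or different in the EHR as a separate record-gap cause. Report its frequency by arm. If the coordinator algorithms already do this, state the rule in the protocol.
2. Keep the primary definition, so that the basis for the 64% is unchanged.
3. Add to F3/F4 one prespecified sensitivity analysis of the medication-error endpoint that excludes record gaps in both arms. Where the transplant physician has corrected a regimen, the corrected regimen is the intended one, so that real vetting is still credited.
4. If the difference between arms shrinks in that analysis, report that part as record reconciliation.

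The cost is one form code and one analysis, with no added patients or visits. Power in the sensitivity analysis falls from 93% to about 87% at a 10% share and 79% at 20%.

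I would not ask the coordinator to flag which EHR entries came from patient report, or add an analysis that ignores them. That would point a blinded assessor to a marker the intervention creates, count pharmacist-vetted drugs as errors, and assume that usual care labels such entries the same way.

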This is an open-label study, so subjects and the research team will be aware of the study assignment. Due to the nature of the intervention, blinding of the subject and research staff is unable to be performed. In order to minimize bias, data for outcomes will be collected by blinded study personnel, as much as feasibly possible.

E Study Procedures

E1 Screening for Eligibility

Adult (≥ 18 years old at the time of transplant) solitary kidney transplant recipients 6 to 36 months post-transplant that meet study eligibility will be approached by research personnel for consideration for participation at the time of a usual care clinic visit or healthcare encounter with the transplant team.

E2 Schedule of Measurements

All patients in both arms of the study will continue to receive usual post-transplant care. The supplemental care that is provided to the intervention group will all be via remote monitoring and televisits, also detailed in section above. In addition, there will be two study specific clinic visits and four televisits that occur in all patients (both control and intervention arms), as detailed in the table below. The Baseline visit will not be counted as a study visit, as this will be the usual care visit patients are identified, screened, consented and randomized at. The table below outlines these visits and what will be assessed during the visits.

Assessment	Base-line	Month 2	Month 4	Month 6	Month 8	Month 10	Month 12
Obtain informed consent, collect baseline patient and transplant information	X						
Assessment for medication errors				X			X
Tele assessment for medication errors		X	X		X	X	
Assessment for adverse drug events				X			X
Tele assessment for adverse drug events		X	X		X	X	
Assessment for health care encounters				X			X
Tele assessment for adverse health care encounters		X	X		X	X	
Chart review assessment for acute rejection(s)	X	X	X	X	X	X	X
Chart review assessment for infection(s)	X	X	X	X	X	X	X
Chart review assessment for graft function, graft loss and death	X	X	X	X	X	X	X

E3 Safety and Adverse Events

3.a Safety and Compliance Monitoring

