8. Costs associated with care will be assessed based on data from hospital accounting at the study institution, once the study is completed. Costs will be measured from the time of randomization up until the end of the 12-month follow-up period. Analyses will include all costs associated with inpatient and outpatient care, including hospitalizations, ambulatory care visits, ambulatory procedure visits, acute care/emergency room visits and laboratory assessments. Costs uniquely associated with the intervention group will include the costs of the devices and data plan provided to the patients, time necessary for training patients on use of the technology and research pharmacist time associated with the intervention. Total costs will be calculated for each cohort. These data will be electronically captured by providing a list of patient's MRNs to hospital accounting after the completion of the study to allow for accurate and complete billing information to accrue. Costs associated with healthcare encounters that occur outside the study institution will be estimated by acquiring information from the patient regarding the type of encounter and using this data to estimate cost based on cost/charge ratios from the study institution. This will be a costs - consequences analysis (CCA) using cost effectiveness methodology, taken from the societal perspective.

F Statistical Plan

F1 Sample Size Determination and Power

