in the relationship between dependent and independent variables, with a lack of serial correlation between covariates, homoscedasticity of the errors and normality of the error distribution, linear regression will be utilized in a similar manner. We will adjust for baseline values if the interventions are discrepant at baseline. This model will include the intervention arm and baseline response as fixed-effects and is known to lead to very precise inference.(7) If any of the four aforementioned assumptions are violated, then the data variables will either be transformed or appropriate substitute multivariable modelling will be used. Cox proportional hazard regression analysis will be used for time-dependent survival analyses involving the outcomes of graft and patient survival. For count outcomes, such as health care encounters, we will use Poisson regression; if the assumption of equal mean and variance is violated (over dispersion), we will use Negative Binomial regression. In all models, we will adjust for correlation of outcomes by including random effect terms. For all models that belong to the generalized linear model (linear, logistic, Poisson), we will use generalized estimating equations (GEE), and for survival outcomes, we will use frailty Cox regression.(8) We will use multiple imputation techniques to deal with missing data that is at random (MAR).(9) MAR assumes that the probability that an outcome is missing depends on observed outcomes. While mechanisms for missingness are likely to be MAR, we will also do sensitivity analysis for data missing not at random (MNAR) using methods from Little and Rubin.(9)

F4 Statistical Methods

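### No pre-randomisation costs or encounters are collected, so an inexpensive gain in precision for Hypothesis 2 is forgone and F3's conditional baseline adjustment has no covariate for costs

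*Combined protocol and SAP*

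**What the plan says.** - **E2, schedule table.** "Assessment for health care encounters" is marked at Months 6 and 12, and "Tele assessment for adverse health care encounters" at Months 2, 4, 8 and 10. Neither row is marked at Baseline. The chart-review rows for rejection, infection and graft outcomes are. The one general Baseline entry is "Obtain informed consent, collect baseline patient and transplant information", which does not name earlier use of care.
- **E4 item 7.** Encounters count only when "occurring within a licensed healthcare facility and occurring during the 12-month study". They are captured by patient interview every two months and include care outside the institution.
- **E4 item 8.** "Costs will be measured from the time of randomization up until the end of the 12-month follow-up period". The source is retrospective: "These data will be electronically captured by providing a list of patient's MRNs to hospital accounting after the completion of the study".
- **F3.** The default comparison is unadjusted (t-test or Mann-Whitney). In the linear-regression text for continuous outcomes, baseline values are adjusted for only if the arms differ on them, and of that model F3 says: "This model will include the intervention arm and baseline response as fixed-effects and is known to lead to very precise inference". Encounters are assigned separately to Poisson regression, or negative binomial if overdispersed.

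**The concern.** Earlier use of care is a natural candidate predictor of later costs and encounters, and F3 itself points to baseline adjustment as a source of precision. Yet the collection windows in E2 and E4 leave that adjustment with nothing to work on for the cost outcome. Nor can anyone check whether the arms were alike in prior cost, which is the condition F3 sets for using the model. For encounters, no prior count is available to enter in the count model.

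F1 plans both Hypothesis 2 comparisons at about 80% power on 52 per arm, so there is little margin. The missing information should largely exist already. The trial is single-centre (H1), patients are recruited from its transplant clinic at 6 to 36 months after transplant (D2), and item 8 already sends every record number to hospital accounting.

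**Working it through.** **1. Is there a baseline value?** E2 has no Baseline mark for encounters, item 7 opens the encounter window with the study, and item 8 opens the cost window at randomisation. Taken together, no pre-randomisation value is planned for either outcome.

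**2. What does F3 need?** The baseline-response model is in the linear-regression text and is conditional. It can apply to costs, where the covariate is absent. It is not the model named for encounters.

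**3. Reproducing F1 for costs.** Inputs from F1: difference $2,489 ($7,658 − $5,169), SD $4,530, two-sided alpha 0.05, 52 per arm.
- Standard error = 4,530 × √(2/52) = 888.4; ratio = 2,489 / 888.4 = 2.80.
- Power = 80.0% (normal approximation) or 79.3% (noncentral t). F1 states more than 80%.
- At 85% retention, 68 × 0.85 = 57.8, so about 58 per arm. Standard error = 4,530 × √(2/58) = 841.2; ratio 2.96; power 83.5% (noncentral t, 114 degrees of freedom).

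**4. Adding a look-back cost covariate.** Residual SD = 4,530 × √(1 − r²), where r is the correlation between look-back and follow-up cost. The documents give no r, so the range is an assumption. Noncentral t, 58 per arm:

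| r | Residual SD ($) | Ratio | Power |
|---|---|---|---|
| 0 (unadjusted) | 4,530 | 2.96 | 83.5% |
| 0.2 | 4,438 | 3.02 | 85.0% |
| 0.3 | 4,321 | 3.10 | 86.8% |
| 0.5 | 3,923 | 3.42 | 92.3% |

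The gains are 1.5, 3.3 and 8.8 points. This treats cost as normal on the raw scale. F3 would send skewed costs to Mann-Whitney, so the table is illustrative.

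**5. Why encounters get no such table.** F1 gives control mean 18.4 and SD 2.6, so the variance is 2.6² = 6.8. A Poisson count with that mean has variance 18.4 and SD √18.4 = 4.3. F1's SD therefore shows no between-patient spread for a prior count to explain.

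As a check, assume Poisson counts within patient and one constant rate per patient, with between-patient relative variance v. A 3-month look-back has mean 18.4 / 4 = 4.6. Then:
- 12-month variance = 18.4 + 18.4²v; 3-month variance = 4.6 + 4.6²v; covariance = 4.6 × 18.4 × v.
- r = 0.3 requires v = 0.050, a 12-month variance of 35.4 and SD 5.9.
- r = 0.5 requires v = 0.123, a 12-month variance of 59.9 and SD 7.7.

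Both SDs are more than twice F1's 2.6. Combining SD 2.6 with r of 0.3 to 0.5 would therefore give a gain that the inputs do not support. Visits on a regular schedule would vary less than Poisson, which softens this, but the documents give nothing with which to quantify it.

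**The case against.** A reader might infer that Hypothesis 2 cannot be analysed as planned. The documents do not support that. The default comparison in F3 is unadjusted, and under randomisation it is valid without a baseline value. The baseline-response model is conditional, reaches costs and not encounters, and can be used elsewhere: graft function has a baseline value in E2 and E4 item 5.

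A reader might also infer that a chance imbalance in heavy users of care could not be corrected at all. That goes too far. F3 allows multivariable adjustment for imbalanced characteristics known to influence outcomes, and baseline rejection, infection and graft-function reviews are scheduled. These are indirect substitutes for prior use, but they exist. Nor is anything lost for good, since the accounting data are drawn after the study.

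Three further objections stand in part:
- The gain depends on an r that the documents do not give. At r = 0.1 it is under half a point for costs.
- Encounters are defined by interview and include care elsewhere. An accounting count would be a differently measured proxy, and item 8 does not say that the extraction can return item 7's categories.
- The attachments are largely absent from the text available for review, so a baseline form that records prior hospital use cannot be ruled out. E4's stated windows would still leave it without a role in the analysis.

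Finally, C2 lists resource use as a secondary aim, which limits the weight of the point.

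**Conclusion.** The point holds as a low-cost improvement and not as a defect in validity. No pre-randomisation costs or encounters are planned. For costs, F3's conditional adjustment therefore has no covariate and its trigger cannot be checked. For encounters, the count model has no prior-use covariate. What is forgone is precision.

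For costs the illustrative size is 1.5 points of power at r = 0.2 up to 8.8 points at r = 0.5, from 83.5%. This rests on F1's difference and SD, 58 analysed per arm, a normal-outcome approximation and an assumed r. For encounters no figure should be claimed. The implausibly small SD in F1 is a separate and larger question for that outcome.

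**What to change.** 1. **E4 item 8:** extend the post-study extraction by record number to a fixed look-back before randomisation, identical in both arms. Three months would serve. Every patient is at least 6 months post-transplant, so the window starts no earlier than 3 months after transplant and should be clear of the transplant admission.
2. **E2:** show the look-back in the Baseline column as a retrospective data item.
3. **F3:** before outcome data are seen, prespecify look-back cost as a covariate in the cost model, whether or not the arms differ on it. Prespecify the look-back institutional encounter count as a covariate in the Poisson or negative binomial model, labelled as a proxy. State the scale on which look-back cost enters.
4. Confirm with hospital accounting that the extraction can return encounter counts. If it cannot, apply the change to costs only.

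The cost is a wider date range in an extraction already planned and one covariate in each of two models, with no added visits or patient contact. Care outside the institution before randomisation would not be seen. That weakens the covariate but, because it is measured before randomisation, does not bias the comparison of arms.
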